8.3. RECORDING

AE data should be obtained through observation of the patient, from any information volunteered by the patient, or through patient questioning.

All AEs encountered during the clinical study, including SAEs will be reported in the appropriate section of the CRF. It is important that this includes the duration of the AE (onset/resolution dates), the relationship to the drug, the severity, and relevant concomitant treatments dispensed (or other action taken) (see Sections 8.3.2., 8.3.3., and 8.3.4. below).

8.3.1. AE reporting period

All AEs which occur during the treatment period (i.e. the first to last day of Investigational Product administration) and up to 10 days after the end of Investigational Product administration or up to hospital discharge, whichever occurs earlier, will be recorded in the CRF.

In addition, any known untoward event that occurs subsequent to the AE reporting period that the Investigator assesses as at least possibly related to the Investigational Product should also be reported as an AE.

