7.8. MONTH 1 POST-TRANSPLANT

Patient will attend the center for study assessment at month 1 (at least 30 days post transplant). The following measurements will be performed as per center practice and recorded in the CRF:

- FEV₁, FVC. Actual date of assessment will be recorded in the CRF.

Any AEs that occurred during the interval i.e. since 10 days after the end of study drug administration or since hospital discharge (if applicable), and that the Investigator assesses as at least possibly related to the Investigational Product, will be recorded at this visit, as well as patient vital status.

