14.4. APPENDIX 4 - STUDY FLOW CHART

Test/Examination	Screening	Tx	ICU admission	Time after ICU admission							ICU discharge	Hospital discharge	1 month	6 months	12 months
				12 h	24 h	36 h	48 h	54 h	60 h	72 h					
Informed consent	X														
Inclusion/exclusion criteria ¹	X														
Laboratory tests	X										X				
Renal/hepatic function ²	X			X ²	X ²	X ³									
Study drug administration ³		X					X ²								
Pharmacokinetic sampling ²					X ²		X ²	X ²							
PaO ₂ /FiO ₂ ratio			X		X		X			X					
Chest X-ray			X		X		X			X					
Vital signs (BP & HR) ⁴	X		X	X	X	X	X		X	X	X				
Cardiopulmonary measurements ⁴			X	X	X	X	X		X	X	X				
BAL ⁵				X ⁵											
Vital status										X	X	X	X	X	
FEV ₁ & FVC												X	X	X	
BOS score													X	X	
Cumulative acute rejection													X	X	
Adverse Events ⁶		X										X ⁶	X	X	X ⁶
Prior and concomitant medications ⁷	X											X ⁷	X	X	X ⁷

1 = Confirmatory screening to take place upon admission to the center prior to randomization

2 = (shadowed boxes) Time is from the start of study drug infusion. The '24 hours' sample is taken @ 24±6 hours; the '54 hours' sample is taken in the interval 2-6 hours after the infusion end

3 = Study drug infusion will start approximately 2 hours before the anticipated time of reperfusion

4 = Vital signs and cardiopulmonary measurements (when a PA catheter is present) will be measured up to ICU discharge or up to 5 days after ICU admission, whichever occurs earlier

5 = BAL will be performed during mechanical ventilation, in the interval between 12 and 24 hours after reperfusion

6 = All AEs will be reported up to 10 days or hospital discharge. Thereafter, only untoward events that the Investigator assesses as at least possibly related to the study drug will be recorded

7 = After 10 days or hospital discharge, only drugs used for immunosuppression, infection prophylaxis, and AEs possibly related to the study drug (see 6 above) will be recorded

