#### 9.6.2 Adverse events

A summary of treatment-emergent adverse events (see Section 5 for definition) reported between start of infusion and the Month 1 visit, including the total number of events reported, the number and percentage of patients reporting at least one adverse event, the number and percentage of patients withdrawing prematurely due to an adverse event, the number and percentage of patients with at least one serious adverse event and the number and percentage of deaths, will be presented by treatment. In addition, a summary of the event by each category of drug relationship will be presented for adverse events and also for serious adverse events.

A breakdown of the number and percentage of patients reporting each adverse event, categorized by body system and preferred term coded according to the MedDRA dictionary, will be presented. Note that counting will be of patients not events and patients are only counted once within each preferred term.

A further tabulation of these data, broken down by relationship to study drug, will be presented. Patients with multiple events within a particular body system or preferred term will be counted under the category of their most drug-related event within that body system or preferred term.

Relationship to study drug is categorized as none, unlikely, possible, probable and highly probable as recorded on the CRF. Each category of relationship will be presented on a separate page.

A summary of events reported, broken down by severity (mild, moderate, severe, life threatening), will also be provided. Patients with multiple events within a particular body system or preferred term will be counted under the category of their most severe event within that body system or preferred term. Each category of severity will be presented on a separate page.

A summary of adverse events leading to premature withdrawal will be provided, grouped by body system and preferred term.

All adverse events recorded on the CRF will be listed.

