### 9.6.3 Serious Adverse Events

A breakdown of the number and percentage of patients reporting each serious adverse event (SAE) between the start of infusion and the Month 1 visit, categorized by body system and preferred term coded according to the MedDRA dictionary, will be presented.

A further tabulation of these data, broken down by relationship to study drug, will be presented. Patients with multiple SAEs within a particular body system or preferred term will be counted under the category of their most drug-related SAE within that body system or preferred term. Relationship to study drug is categorized as none, unlikely, possible, probable and highly probable as recorded on the CRF. Each category of relationship will be presented on a separate page.

A summary of SAEs reported, broken down by severity (mild, moderate, severe, life threatening), will also be provided. Patients with multiple SAEs within a particular body system or preferred term will be counted under the category of their most severe SAE within that body system or preferred term. Each category of severity will be presented on a separate page.

A summary of SAEs leading to premature withdrawal will be provided, grouped by body system and preferred term.

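### The SAP reports AE incidence to Month 1 as one figure, but the protocol requires all-cause recording only to about day 12 at the latest, or to discharge if earlier

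*Protocol*

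**What the plan says.** Protocol 8.3.1 records all AEs during the infusion and then "up to 10 days after the end of Investigational Product administration or up to hospital discharge, whichever occurs earlier". Beyond that point it asks only for "any known untoward event that occurs subsequent to the AE reporting period that the Investigator assesses as at least possibly related" to the study drug. Section 7.8 applies the same restriction at Month 1: AEs from the interval "that the Investigator assesses as at least possibly related to the Investigational Product, will be recorded at this visit". Footnote 6 of the flow chart (Appendix 4) gives the limit in shorter form, "All AEs will be reported up to 10 days or hospital discharge", without saying that the earlier of the two applies.

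SAP 9.6.2 defines its summary as covering treatment-emergent AEs "reported between start of infusion and the Month 1 visit, including the total number of events reported". SAP 9.6.3 covers SAEs "between the start of infusion and the Month 1 visit, categorized by body system and preferred term". SAP section 5 puts Month 1 at day 30 to 35 after transplant. Both sections also tabulate events by relationship, from none to highly probable. Neither mentions a change of capture rule or days at risk, and SAP 1.2 declares no changes from the protocol. Listings 2.7.1 and 2.7.2 carry Month 1 in their titles; the AE table titles in SAP section 11 state no window.

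Two other protocol sections bear on the point. Section 8.3 sends all AEs during the study, SAEs included, to the CRF. Section 8.4.1 requires every SAE to be reported whatever its presumed cause. Neither gives an end date.

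**The concern.** An incidence described as running to Month 1 will be read as all-cause incidence over a month, which is more than 8.3.1 requires sites to collect. Three things follow.

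- **Unlike periods in one table.** Counts for none and unlikely are assured only to the end of the 8.3.1 window, while counts for possible and above run to Month 1. The distribution by relationship shifts towards related events for a reason that has nothing to do with the drug.
- **A window that can end at an outcome.** Discharge comes after randomization and follows recovery. If treatment changes time to discharge, it also changes how long all-cause events are collected.
- **Deaths.** SAP 9.6.2 asks for the number of deaths, and the shell for Table 3.2.1.1 shows AEs leading to death. A late death from an event judged unrelated might be missing from that row yet counted in the 30-day mortality table of SAP 9.5.2.5.

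Safety is a stated objective of the trial. The primary endpoint is not affected.

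**Working it through.** The plan states no figure on this point, so there is none to reproduce. The check compares the windows and then illustrates what they could do.

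**Inputs.** Infusion of 48 hours, or 2 days (Protocol 3.1). A further 10 days or discharge, if earlier (Protocol 8.3.1). Month 1 at day 30 to 35 after transplant (SAP 5). Infusion starts about 2 hours before reperfusion, so counting days from infusion or from transplant makes no material difference.

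**Length of full capture.**
- Latest end: 2 + 10 = day 12.
- Share of the period to Month 1: 12/30 = 40%; 12/35 = 34%.
- Remaining related-only period: 30 − 12 = 18 days (60%) to 35 − 12 = 23 days (66%).
- If the infusion stops at 12, 24 or 36 hours, the limit falls at day 10.5, 11.0 or 11.5. Discharge before the limit ends full capture sooner.

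**What is collected when.**

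| Event | Within the 8.3.1 window | From then to Month 1 |
|---|---|---|
| AE judged none or unlikely | recorded | not required by 8.3.1 or 7.8 |
| AE judged possible or higher | recorded | recorded |
| SAE judged none or unlikely | recorded | unclear: 8.3.1 against 8.3 and 8.4.1 |
| Death to day 30 | recorded | captured through vital status |

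**Illustration for events not judged related.** The documents give no AE rates and no lengths of stay, so every risk and discharge day here is an assumption. With true 30-day risk R and constant hazard, λ = −ln(1 − R)/30, and the risk recorded by day t is p(t) = 1 − exp(−λt). For R = 30%, λ = 0.357/30 = 0.0119 and p(12) = 1 − exp(−0.143) = 13.3%. If instead 75% of the cumulative hazard falls in the first 12 days, the recorded risk is 1 − (1 − R)^0.75.

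| True 30-day risk | To day 12, constant hazard | To day 8, constant hazard | To day 12, 75% of hazard early |
|---|---|---|---|
| 10% | 4.1% | 2.8% | 7.6% |
| 30% | 13.3% | 9.1% | 23.5% |
| 50% | 24.2% | 16.9% | 40.5% |

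**Difference between arms from the window alone.** Take equal true hazards (constant), a share s discharged at day 8, and the rest captured to day 12. The recorded risk is s·p(8) + (1 − s)·p(12). With s = 50% in one arm and 25% in the other, and R = 30%, this gives 11.2% against 12.2%, a gap of 1.1 points before rounding. For R = 10% and 50% the gaps are 0.3 and 1.8 points. In the extreme case of s = 100% against 0%, the gaps are 1.4, 4.2 and 7.3 points for R = 10%, 30% and 50%. In each case the arm discharged earlier shows the lower risk.

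**The case against.** The SAP tells its reader to use it together with the protocol, where the capture rule is explicit. Events judged at least possibly related are still collected to Month 1. Onset dates are recorded, all AEs are listed, and the safety analysis is descriptive, so no test is biased. All of that stands. It does not make the SAP's stated window match the data collected, and a listing does not correct a summary table.

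Several stronger readings are tempting and are not supported:

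- **That the SAE tables must under-count.** Protocol 8.4.1 requires all SAEs with no end date, and 8.3 sends SAEs to the CRF. The SAP does not say whether CRF or pharmacovigilance data feed the SAE tables. The gap may or may not arise, depending on which rule sites follow.
- **That the deaths row will contradict the mortality table.** It may. A death is itself an SAE, vital status is recorded at Month 1, and a death report listing is planned, so mortality is not lost. The two tables also differ by design: Safety population to the Month 1 visit, against ITT to 30 days after the latest reperfusion. They could differ even with complete capture.
- **That some 60% of AEs are missed.** The 60 to 66% is calendar time. Events after surgery and a 48-hour infusion may well come early, and the early-hazard column shows a much smaller loss.
- **That repertaxin will look safer.** This needs a difference in discharge before about day 12, and the documents give no length-of-stay data.
- **That the AE tables are titled to Month 1.** Only the SAP text and the two listing titles say so.

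**Conclusion.** The point holds for AEs. Followed as written, the SAP combines all-cause events from at most about 12 days with related-only events from the following 18 to 23 days and presents them as one incidence. The all-causality and by-relationship tables can under-count late events judged unrelated or unlikely, and a patient's all-cause window can end at discharge. The 12-day limit follows directly from the documents. The number of events lost, and the size and direction of any bias between arms, cannot be derived from them; the illustrated risks rest on assumed hazards and discharge days.

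For SAEs and deaths, the documents establish an unresolved inconsistency between protocol sections and an unstated data source. They do not establish a definite under-count.

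This should be corrected before database lock. It changes what the safety tables report.

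**What to change.** In SAP 9.6.2 and 9.6.3:

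1. Restrict the all-causality and by-relationship AE tables to the 8.3.1 full-capture window for each patient, derived from recorded onset, infusion-end and discharge dates, and state that window in the titles.
2. Put later events judged at least possibly related in a separate table.
3. Show days of full capture by arm, with incidence per patient-day as support.
4. Take the deaths count in the AE summary from Month 1 vital status and the death report. Footnote how its population and period differ from the 30-day mortality table.
5. State which source feeds the SAE tables.

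In the protocol, reconcile 8.3, 8.3.1, 8.4.1 and flow chart footnote 6 on the capture period, for SAEs in particular. About 60 patients had been randomized when this SAP version was written, so a longer SAE period applied only to later patients would again put two rules in one table. Whichever period is settled on, each table should apply one rule to all its patients, using the common window if late unrelated SAEs cannot be recovered for earlier patients.

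The SAP part costs a window flag and one or two extra tables. It needs no new visit and no new data, and SAP 1.1 leaves the plan open to finalization until database lock. The reconciliation needs a short protocol clarification.

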8.3.2. Relationship of AEs to the Investigational Product

The Investigator will assess the possible relationship between the AE and the investigational medication, according to the criteria in Table 1 below:

Table 1: Relationship of the Adverse Event to the Investigational Product

None (Intercurrent Event)	An event that is not and cannot be related to the Investigational Product, e.g. patient is a passenger in a road traffic accident
Unlikely (remote)	Relationship is not likely e.g. a clinical event including laboratory test abnormality with temporal relationship to drug administration which makes a causal relationship improbable and in which other drugs, chemicals or underlying disease provide plausible explanations
Possible	Relationship may exist, but could have been produced by the patient's condition or treatment or other cause
Probable	Relationship is likely, the AE abates upon discontinuation of Investigational Product and cannot be due to the patient's condition
Highly Probable	Strong relationship, the event abates upon discontinuation of Investigational Product and, if applicable, re-appears upon repeat exposure

An **Adverse Drug Reaction (ADR)** is defined as an adverse experience which is a reasonably likely to have been caused by the drug. Any AE reported in the study having a possible, probable or highly probable relationship to study drug will be considered as an ADR.

8.3.3. Severity of AEs

The Investigator will grade the severity of any AE using the definitions in Table 2. For each episode, the highest severity grade attained should be reported.

Table 2: Severity of the Adverse Event

Mild	Grade 1 - Does not interfere with patient's usual function (awareness of symptoms or signs, but easily tolerated [acceptable]).
Moderate	Grade 2 - Interferes to some extent with patient's usual function (enough discomfort to interfere with usual activity [disturbing]).
Severe	Grade 3 - Interferes significantly with patient's usual function (incapacity to work or to do usual activities [unacceptable])
Life Threatening	Grade 4 - Results in risk of death, organ damage, or permanent disability [unacceptable]

8.3.4. Frequency of AEs

The frequency of AEs should be described as per Table 3.

Table 3: Frequency of the Adverse Event

Once	The AE occurred only once and resolved in < 24 hours
Occasionally	The AE occurred sporadically or episodically between the onset and resolution dates (and times)
Continuously	The AE was present for the entire time between onset and resolution dates (and times) and was > 24 hours duration

8.4. SERIOUS ADVERSE EVENT REPORTING

8.4.1. Reporting Procedure for Investigators to PPD

The Investigator must report all SAEs, regardless of presumed causal relationship, to the PPD Pharmacovigilance Department, by fax within 24 hours of learning of the event. Details of the relevant fax number for SAE reporting are provided in the section "Contact Information".

Information on SAEs will be recorded on a specific Non-Carbon Repeat SAE form. Blank copies will be included in the Investigator's Site File.

Follow-up reports (as many as required) should be completed and faxed following the same procedure above.

A final report is required in any case once the condition is resolved or stabilized and no more information about the event is expected. The final report should be completed and faxed following the same procedure above.

PPD will report to Dompé all information received by the Investigators, by fax within 24 hours of knowledge.

8.4.2. Reporting Procedure for Investigators to IRB/REB

In addition to reporting the SAE to PPD, the Investigator must also comply with the requirements related to the reporting of SAEs to the IRB/REB which approved the study.

The requirements of IRB/REB varies from one state and indeed one country to another, however as a minimum requirement all Investigators must promptly report all serious unexpected* ADRs, life-threatening problems or deaths to their IRB/REB.

PPD will inform Investigators of all serious unexpected ADRs, which are reported to PPD from other Investigators. These SAEs should also be reported promptly to the IRB/REB in compliance with the local regulations. Copies of all correspondence relating to reporting of any SAEs to the IRB/REB should be maintained in the Investigator's Files and provided to PPD.

* An **unexpected ADR** is defined as any adverse drug experience, the nature or severity of which is not consistent with the current Investigator's Brochure.

8.4.3. Reporting Procedure for Regulatory Authorities

This study is intended to take place at centers in the USA and Canada and therefore should satisfy both FDA and Health Canada SAE reporting requirements.

During the course of the clinical trial, Dompé (or designee) shall inform FDA/Health Canada of any serious unexpected ADR as soon as possible and in no event later than:

- (a) seven calendar days after becoming aware of the information if it is fatal or life threatening; and
- (b) fifteen calendar days after becoming aware of the information if it is neither fatal nor life threatening.

Dompé (or designee) shall, within eight days after having informed Health Canada under paragraph (a), submit a complete report in respect of that information that includes an assessment of the importance and implication of any findings made.

Furthermore Dompé shall promptly investigate all safety information received by it and follow up information to a safety report shall be submitted to the appropriate authorities as soon as the relevant information is available.

If the results of an investigation show that an adverse drug reaction not initially determined to be reportable is reclassified as reportable, Dompé (or designee) shall report such reaction in a written safety report as soon as possible, but in no event later than 15 calendar days after the determination is made.

8.5. DATA MONITORING COMMITTEE

An independent Data Monitoring Committee (DMC) will be established to ensure patient safety, to consider patient risks against the potential for meeting trial objectives, and to provide recommendations to Dompé with respect to the conduct and analysis of the trial. The DMC will operate independently of Dompé, and its members will not have connections to the Sponsor with the exception of the compensation to DMC members related to DMC activities.

The DMC will comprise three voting members. They will be a multidisciplinary group that will include:

- A surgeon with extensive experience in lung transplantation,
- A physician with relevant experience in pulmonary and critical care medicine (e.g. a Medical Director of a Lung Transplant Program),
- A biostatistician.

The DMC will perform the following major functions:

- The DMC will be responsible for the ongoing review of safety data throughout the trial. Primary among the safety data that will be reviewed are serious AEs, ADRs and relevant available clinical laboratory results.
- The DMC may review acute and additional safety data, on a patient-by-patient basis, at their discretion. This review would be warranted if significant unexpected ADRs are observed.
- The DMC may request additional safety data if, in the view of the Committee, these additional data are needed in order to make an informed, responsible decision about the conduct of the study.
- The DMC will advise Dompé regarding safety of patients and continuing validity and scientific merit of the trial. The DMC will also monitor the number of deaths for both arms of the study to ensure that mortality is consistent with historical data.

All details of the conduct and responsibilities of the study DMC will be described in the 'DMC Charter' which will be finalized prior to the start of patient enrolment.

9. STATISTICAL ISSUES

9.1. SAMPLE SIZE

The sample size has been estimated based on PaO₂/FiO₂ ratios immediately and at 24 hours from the results of 700 lung transplant operations at the Washington University. The database reports means and standard deviations for this endpoint of 329±137 mmHg at the initial ICU assessment and 315±117 mmHg at 24 hours.

A sample size of 50 in each group will have a 81% power to detect a difference in means of 70 mmHg (the difference between a placebo mean of 315 and a treated mean of 385, a 22% improvement) assuming that the common standard deviation is 137 using a two group t-test with a 0.05 one-sided significance level. Alternatively, a sample size of 50 in each group will have a 56% power to detect a difference in means of 50 mmHg (the difference between a placebo mean of 315 and a treated mean of 365, a 15% improvement) assuming that the common standard deviation is 137 using a two group t-test with a 0.05 one-sided significance level.

There is no currently available data to provide a knowledgeable estimate of the effect size in this study. If the effect size is smaller than 15%, the power of this study will be reduced and the chance of a Type II error is increased. Under such circumstances, this study would still provide valuable data regarding the effect size in the primary outcome variable as well as the results in all of the secondary, exploratory endpoints and subgroup analysis.

